#### **6.14. Analysis for Submission to Japan - Regulatory Body**

A subset of the planned efficacy and safety analyses will be summarized based on patients from Asian sites (Japan and Korea), in support of the regulatory submission in Japan. The list of tables, listings, and figures for the patients from Asian sites (Asian population) will be in a separate document.

In addition, a by-patient listing of patients from Asian sites with the number of self-injections will be provided for Period 2. The self-injection is defined as the injection administered either by study subject or by caregiver during Period 2.

#### **6.15. Subgroup Analyses**

##### **6.15.1. Efficacy Subgroup Analyses**

Subgroup analysis will be conducted for the primary endpoints of proportion of patients achieving an ASAS40 response at Weeks 16 and 52 (NRI) using the ITT Population for the Period 2. The proportion of patients achieving ASDAS <2.1 (NRI) at Weeks 16 and 52, will also be conducted.

For ASAS40, ASDAS <2.1, a logistic regression analysis with treatment, subgroup, and treatment-by-subgroup interaction as factors will be used. The treatment-by-subgroup interaction will be tested at the 10% significance level. Treatment group differences will be evaluated within each subgroup using the Fisher's exact test, regardless of whether the interaction is statistically significant. If any group within the subgroup (for example, yes, no) is <10% of the total population, only descriptive statistics will be provided for that subgroup (that is, no inferential testing).

Forest plots may be created to illustrate the treatment differences with 95% CIs between each of the ixekizumab treatment groups and placebo group, by each subgroup category.

The following subgroups will be analyzed:

- Patient Demographics Subgroups:
  - Sex
  - Age category: <40 years, ≥40 years
  - Age category: <50 years, ≥50 years
  - Age category: <65 years, ≥65 years
  - Weight: <70 kg, ≥70 kg
  - BMI: underweight (<18.5 kg/m^2); normal (≥18.5 and <25 kg/m^2); overweight (≥25 and <30 kg/m^2); obese (≥30 and <40 kg/m^2); or extreme obese (≥40 kg/m^2)
  - Ethnicity: Hispanic/Latino, Non-Hispanic/Non-Latino

- Race: American Indian/Alaska Native, Asian, Black/African American, Native Hawaiian or other Pacific Islander, White, or Multiple
- Geographic Region Subgroups:
  - Geographic region: Europe, non-Europe
  - Geographic region: America, Asia, Europe
  - Geographic region: North America (US, including Puerto Rico if any, Canada) or Rest of the World
  - Geographic region: US (including Puerto Rico if any), non-US
  - Geographic region: South America (Argentina, Brazil and Mexico), Rest of the World (non-South America)
- Baseline Severity of Disease Subgroups:
  - Baseline CRP categories:
    - $\leq 3.00$  mg/L or  $> 3.00$  mg/L
    - $\leq 5.00$  mg/L or  $> 5.00$  mg/L
    - $\leq 10.00$  mg/L or  $> 10.00$  mg/L
    - $\leq 15.00$  mg/L or  $> 15.00$  mg/L
  - Baseline MRI status:
    - SPARCC SIJ score  $\geq 2$  or  $< 2$
  - Screening MRI/CRP status:
    - positive MRI and elevated CRP
    - positive MRI and nonelevated CRP
    - negative MRI and elevated CRP

*Note: Positive MRI is defined by Assessment of SpondyloArthritis international Society/ Outcome Measures in Rheumatology Clinical Trials (ASAS/OMERACT) criteria and elevated CRP is defined as  $> 5.00$  mg/L.*
  - Baseline BASDAI:
    - $4 \leq \text{BASDAI} < 6$  or  $\text{BASDAI} \geq 6$
  - Baseline ASDAS:
    - $\text{ASDAS} \leq 3.5$  or  $\text{ASDAS} > 3.5$
- Other Patient Characteristics Subgroups:
  - Duration of symptom since AxSpA onset category:  $< 10$  years or  $\geq 10$  years
  - Duration of symptom since AxSpA onset category:  $< 5$  years or  $\geq 5$  years
  - Duration of symptom since AxSpA onset category:  $< 3$  years or  $\geq 3$  years
  - HLA-B27 status: positive or negative
  - Smoking status: current or former/never
  - Concomitant cDMARDs (methotrexate, sulfasalazine, hydroxychloroquine) at baseline: yes or no
  - History of arthritis: yes or no
  - History of uveitis: yes or no
  - History of dactylitis: yes or no
  - History of psoriasis: yes or no
  - History of enthesitis: yes or no
  - History of inflammatory bowel disease: yes or no

- History of extra-axial involvement: yes or no
- Baseline analgesics use: yes or no

Additional subgroup analyses on efficacy may be performed as deemed appropriate and necessary.

### **6.15.2. Safety Subgroup Analyses**

Safety subgroup analysis for common TEAEs and AESI of infections will be summarized by treatment group and overall, using Safety Population for Period 2 using Spotfire. The common TEAEs will be presented by MedDRA PT within SOC. The AESI of infection will be presented by PT.

A logistic regression model with treatment, subgroup, and the interaction of subgroup-by-treatment included as factors will be used. The subgroup-by-treatment interaction will be tested at the significance level of 0.10. The response variable will be each AE. Treatment group differences will be evaluated within each category of the subgroup using Fisher's exact test, regardless of whether the interaction is statistically significant. If any group within the subgroup is less than 10% of the total population, only the descriptive statistics will be provided for that subgroup (that is, no inferential testing).

The subgroups include baseline demographics and geographic region, and are defined in Section [6.15.1](#).

Additional subgroup analyses on safety may be performed as deemed appropriate and necessary.

A large, bold, red graphic consisting of the letters 'C', 'C', and 'I' in a stylized, sans-serif font. The letters are set against a solid black rectangular background.

### **6.16. Protocol Deviations**

Protocol deviations will be identified throughout the study. Important protocol deviations are defined as those violations from the protocol likely to have a significant impact on the completeness, accuracy, and/or reliability of the study data or that may significantly affect a subject's rights, safety, or well-being.

[Table RHBX.6.12](#) includes the categories and subcategories of important protocol deviations, whether or not these deviations will result in the exclusion of patients from PPS, the source of

identification for the deviations, and the statistical programming guidance for the clinical study report (CSR).

The number and percentage of patients having important protocol deviations (s) will be summarized within category and subcategory of deviations by treatment group for:

- Period 2 prior to initiation of biologic rescue of ixekizumab 80 mg Q2W (ITT Population)
- Period 2 post initiation of biologic rescue of ixekizumab 80 mg Q2W (IR Population)

A by-patient listing of important protocol deviations will be provided.

Table RHBX.6.12. Identification and Action of Important Protocol Deviations

Important Protocol Deviation Category/Subcategory/Study Specific	Action for PPS Analysis	Source to Identify Protocol Deviation a
Category: Eligibility		
Subcategory: Inclusion/Exclusion		
[1] Not meeting 'sacroiliitis on MRI and have at least 1 SpA feature'; and not meeting 'positive for HLA-B27 and have at least 2 additional SpA features' at screening	Exclude from PPS	Monitor and Stats
[2] History of back pain <3 months or age at onset ≥45 years	Exclude from PPS	Monitor
[3] No active nonrad-axSpA defined as BASDAI ≥4 and total back pain ≥4 on an NRS at screening and baseline	Exclude from PPS	Monitor and Stats
[4] Not have objective signs of inflammation by presence of sacroiliitis on MRI and not have elevated CRP (defined as CRP >5.00 mg/L).	Exclude from PPS	Monitor and Stats
[5] Not have had an inadequate response to 2 or more NSAIDs at therapeutic dose range for a total duration of at least 4 weeks AND not have history of intolerance to NSAID (for Japan patients, not have had NSAID or had 1 NSAID for a duration of less than 12 weeks)	Exclude from PPS	Monitor
[6] Not have a history of prior therapy for axSpA of at least 12 weeks prior to screening	Exclude from PPS	Monitor
[7] Not ≥18 years of age at time of screening	Exclude from PPS	Monitor and Stats
[8] Female patient of childbearing potential with positive pregnancy test; or did not use a reliable method of birth control, if applicable	Do not exclude from PPS	Monitor and Stats
[10] Fulfillment of the mNY criteria with sacroiliitis defined radiographically, based on central reading	Exclude from PPS	Monitor and Stats
[11] Have a history of other systemic inflammatory diseases or other chronic pain conditions that might confound the evaluations of benefit from ixekizumab therapy	Exclude from PPS	Monitor
[12] Have active Crohn's disease (CD) or active ulcerative colitis (UC) at screening	Do not exclude from PPS	Monitor and Stats
[13] Have evidence of active anterior uveitis (an acute episode) within the last 4 weeks prior to baseline randomization	Do not exclude from PPS	Monitor and Stats
[14] Have current or a history of lymphoproliferative disease, or signs or symptoms of lymphoproliferative disease; or have active or history of	Do not exclude from PPS	Monitor

Important Protocol Deviation Category/Subcategory/Study Specific	Action for PPS Analysis	Source to Identify Protocol Deviationa
malignant disease within 5 years prior to Visit 2		
[15] Have had fluid overload, MI or new onset ischemic heart disease, uncompensated heart failure, or other serious cardiac disease within 12 weeks prior to Visit 2	Do not exclude from PPS	Monitor
[16] Presence of significant, uncontrolled cerebro-cardiovascular events at screening	Do not exclude from PPS	Monitor
[17] Presence of respiratory, hepatic, renal, gastrointestinal, endocrine, hematologic disorder at screening that pose unacceptable risk to patient or with interpretation of data	Do not exclude from PPS	Monitor
[18] Presence of neurologic or neuropsychiatric disorders at screening that pose unacceptable risk to patient or with interpretation of data	Do not exclude from PPS	Monitor
[19] Presence of significant uncontrolled neuropsychiatric disorder, recent history (30 days prior to V1 and anytime between V1 and V2) of a suicide attempt, have a score of 3 on Item 12 (Thoughts of Death or Suicide) of the QIDS-SR16 at Visit 1 or Visit 2, or at risk for suicide	Do not exclude from PPS	Monitor and Stats
[20] In the past 12 weeks prior to V2, had a serious infection, hospitalization or IV antibiotics for an infection; in the past 24 weeks prior to V2, had a serious bone or joint infection; ever had an infection of an artificial joint, or infection that occurs in increased incidence in an immunocompromised host. Japan patients with a positive beta-D-glucan test at screening and a confirmed diagnosis of PCP.	Do not exclude from PPS	Monitor
[21] Have a known immunodeficiency or are immunocompromised to an extent such that participation in the study would pose an unacceptable risk to the patient	Do not exclude from PPS	Monitor
[22] Have or had a herpes zoster or any other clinically apparent varicella-zoster virus infection within 12 weeks of Visit 2	Do not exclude from PPS	Monitor
[23] Have any other active or recent infection within 4 weeks of Visit 2 that would pose an unacceptable risk to the patient	Do not exclude from PPS	Monitor
[24] Have a known allergy or hypersensitivity to any biologic therapy that would pose an unacceptable risk to the patient if participating in this study	Exclude from PPS	Monitor
[25] Have had surgical treatment of a joint to be assessed in the study within 8 weeks prior to baseline randomization or will require such	Exclude from PPS depending on the clinical significance	Monitor

Important Protocol Deviation Category/Subcategory/Study Specific	Action for PPS Analysis	Source to Identify Protocol Deviation a
during the first 16 weeks of the trial		
[26] Had any major surgery within 8 weeks prior to Visit 2, or will require such during the study that would pose an unacceptable risk to the patient	Do not exclude from PPS	Monitor
[27] Not have stable dose for NSAID or COX-2 for at least 2 weeks prior to baseline randomization, if taking NSAID or Cox-2 inhibitors	Only Exclude from PPS if: 1. Stopped or decreased dose for a current med <3 days before randomization; or 2. Start or increased dose for a current med or started a new med <2 wks before randomization	Monitor and Stats
[28] Have received cDMARDs, and/or other therapies such as but not limited to: gold salts, cyclosporine, azathioprine, dapsone, 6-mercaptopurine, mycophenolate mofetil, or any other immunosuppressive agents within 4 weeks prior to baseline randomization.	Exclude from PPS if: 1. Stopped or decreased dose for a current med ≤3 days before randomization; or 2. Started new treatment or increased dose for current med or started a new med <4 wks before randomization.  Patients with Combo cDMARD drug use will be removed from PPS	Monitor and Stats
[29] Current use of oral corticosteroids >10 mg/day prednisone or its equivalent	Exclude from PPS if: 1. Dose >10 mg/day any time within 4 weeks; or 2. Stopped or decreased dose for a current med <10 days before randomization; or 3. Started new treatment or increased dose for current one or started a new one <4 wks before randomization	Monitor and Stats
[30] Have received any prior, or are currently receiving, treatment with biologic or other immunomodulatory agents, including investigational therapies (such as but not limited to Janus kinase (JAK) inhibitors, TNF inhibitors, IL-1, IL-6, IL-23, IL-17 (including ixekizumab), IL-17R, T	Exclude from PPS	Monitor and Stats

Important Protocol Deviation Category/Subcategory/Study Specific	Action for PPS Analysis	Source to Identify Protocol Deviation a
cell, or B cell targeted therapies).		
[31] Are currently enrolled in, have participated, or discontinued from a clinical trial involving an investigational product or nonapproved use of a drug or device within the last 30 days prior to screening or a period of at least 5 half-lives of the last administration of the drug, whichever is longer	Exclude from PPS	Monitor
[32] Are currently enrolled in any other clinical trial involving an investigational product or any other type of medical research judged not to be scientifically or medically compatible with this study	Exclude from PPS	Monitor
[33] Are currently receiving or have received treatment with denosumab within 6 months prior to baseline randomization	Do not exclude from PPS	Monitor and Stats
[34] Have received any parenteral glucocorticoid administered by intra-articular, intramuscular, or IV injection within 6 weeks prior to baseline randomization, or a parenteral injection of glucocorticosteroids is anticipated during the Period 2.	Exclude from PPS	Monitor and Stats
[35] Use of any opiate analgesic at average daily doses >30 mg/day of morphine or its equivalent or use of variable doses of any opiate analgesic within 6 weeks prior to baseline randomization. For Japan patients, use of pregabalin >300 mg/day or use of variable doses of pregabalin within 2 weeks prior to baseline randomization.	Exclude from PPS if: 1. Doses >30 mg/day any time within 6 weeks before randomization; or 2. Stopped or decreased dose for a current one <7 days before randomization; or 3. Started new treatment or increased dose for current one or started a new one <6 wks before randomization	Monitor and Stats
[36] Had a live vaccination or participated in a vaccine clinical study within 12 weeks prior to Visit 2, or intend to have a live vaccination during the study or within 12 weeks of completing study treatment	Do not exclude from PPS	Monitor
[37] Had a vaccination with BCG within 12 months prior to Visit 2, or intend to have this vaccination with BCG during the study or within 12 months of completing study treatment	Do not exclude from PPS	Monitor and Stats
[38] Have a body temperature $\geq 38^{\circ}\text{C}$ (100.5°F) at Visit 2	Do not exclude from PPS	Monitor and Stats
[39] Have evidence or suspicion of active or latent TB	Do not exclude from PPS	Monitor
[40] Are positive for human immunodeficiency virus serology (HIV)	Do not exclude from PPS	Monitor and Stats

Important Protocol Deviation Category/Subcategory/Study Specific	Action for PPS Analysis	Source to Identify Protocol Deviation a
[41] Have evidence of or test positive for hepatitis B virus (HBV) and are HBV DNA positive	Do not exclude from PPS	Monitor and Stats
[42] Have evidence of or test positive for hepatitis C virus (HCV)	Do not exclude from PPS	Monitor and Stats
[43] Have ECG abnormalities that are considered clinically significant and would pose an unacceptable risk to the patient if participating in the study	Do not exclude from PPS	Monitor
[44] Patients having contraindications to MRI	Do not exclude from PPS	Monitor
[45] At Visit 1, have a neutrophil count <1.50 GI/L	Do not exclude from PPS	Monitor and Stats
[46] At Visit 1, have a lymphocyte count <0.80 GI/L; for Japan patients, lymphocyte count <1.0 GI/L	Do not exclude from PPS	Monitor and Stats
[47] At Visit 1, have a platelet count <100 GI/L	Do not exclude from PPS	Monitor and Stats
[48] At Visit 1, have aspartate aminotransferase (AST) or alanine aminotransferase (ALT) >2.5 times the upper limit of normal (ULN)	Do not exclude from PPS	Monitor and Stats
[49] At Visit 1, have a total white blood cell (WBC) count <3.00 GI/L; for Japan patients, WBC count <4.0 GI/L	Do not exclude from PPS	Monitor and Stats
[50] At Visit 1, have hemoglobin <8.5 g/dL for male patients and <8.0 g/dL for female patients	Do not exclude from PPS	Monitor and Stats
[51] Have other clinical laboratory test results at Visit 1 that are outside the normal reference range for the population and are considered clinically significant	Do not exclude from PPS	Monitor
[52] Have donated >450 mL of blood within the last 4 weeks prior to Visit 1, or intend to donate blood during the course of the study	Do not exclude from PPS	Monitor
[53] Are women who are lactating or breastfeeding	Do not exclude from PPS	Monitor
[54] Are investigator site personnel directly affiliated with this study and/or their immediate families	Exclude from PPS	Monitor
[55] Are Lilly employees or its designee or are employees of third-party organizations (TPOs) involved in the study	Exclude from PPS	Monitor
[56] Are unwilling or unable to comply with the use of a data collection device to directly record data from the patient	Exclude from PPS when occurred in Period 2 prior to use of rescue ixekizumab 80 mg Q2W	Monitor
[57] Have any other condition that precludes the patient from following and completing the protocol	Exclude from PPS	Monitor

Important Protocol Deviation Category/Subcategory/Study Specific	Action for PPS Analysis	Source to Identify Protocol Deviationa
Subcategory: other		
Rescreened patients were screened but did not meet rescreening criteria per protocol	Do not exclude from PPS	Monitor
Category: Study Procedures		
Subcategory: Violation of Discontinuation Criteria		
[D1] Lilly medical not consulted when patient met hepatic lab criteria for consideration of discontinuation. For patients from German sites, not discontinued IP for abnormal liver tests.	Do not exclude from PPS	Monitor
[D2-N] Neutrophil counts <0.50 GI/L, or ≥0.50 GI/L and <1.00 GI/L based on 2 test results within 1 week of knowing 1st result, or ≥1.00 GI/L and <1.50 GI/L based on 3 test results and a concurrent infection	Do not exclude from PPS	Monitor and Stats
[D2-W] Total WBC count <2.00 GI/L	Do not exclude from PPS	Monitor and Stats
[D2-L] Lymphocyte count <0.50 GI/L	Do not exclude from PPS	Monitor and Stats
[D2-P] Platelet count <50 GI/L	Do not exclude from PPS	Monitor and Stats
[D3] patient experiences a severe AE, an SAE, or a clinically significant change in a laboratory value that merits the discontinuation of the investigational product and appropriate measures being taken.	Do not exclude from PPS	Monitor
[D4] Clinically significant systemic hypersensitivity reaction does not respond to treatment	Do not exclude from PPS	Monitor
[D5] Patient became pregnant	Do not exclude from PPS	Monitor
[D6] Patient developed a malignancy (Patients may be allowed to continue if they develop no more than 2 nonmelanoma skin cancers during the study for non-German patients). For patients from German site, any malignancy	Do not exclude from PPS	Monitor
[D7] Enrolled in prohibited medical research	Exclude from PPS when occurred in Period 2 prior to use of rescue ixekizumab 80 mg Q2W	Monitor
[D11] Lilly stopped the patient participation	Do not exclude from PPS	Monitor
[D12] Patient became HBV DNA positive	Do not exclude from PPS	Monitor
[D13] Patient has a confirmed diagnosis of PCP during the study for patients from Japan sites; Patients develop a severe infection for patients from German sites	Do not exclude from PPS	Monitor and Stats

Important Protocol Deviation Category/Subcategory/Study Specific	Action for PPS Analysis	Source to Identify Protocol Deviationa
Category: Study Procedures		
Subcategory: Excluded Con-meds		
	Exclude from PPS (Excluded Con-meds refers to clinically meaningful change in con-meds ( Appendix 13 ) occurred during Period 2 prior to use of rescue ixekizumab 80 mg Q2W and prescribed for primary study condition)	Monitor and Stats
Subcategory: Lab/Imaging Criteria		
Missing imaging as per protocol schedule of events	Do not exclude from PPS	Monitor
Missing lab chemistry and hematology: missing baseline or not having at least 1 post-baseline	Do not exclude from PPS	Stats
Subcategory: Other		
Missing QIDS total score: missing baseline or any scheduled visit prior to discontinuation visit	Do not exclude from PPS	Stats
Missing Columbia scale at any visit except Visit 1	Do not exclude from PPS	Monitor and Stats
Missing ASAS components for ASAS40 derivation: not having Week 16 measurement for patients who have completed week 16	Do not exclude from PPS. Note: if missing ASAS components lead to missing ASAS40, such patient will be treated as non-responder for the Week 16 ITT analyses	Stats
Had unqualified site personnel perform clinical safety and/or efficacy assessments	Do not exclude from PPS	Monitor
Category: Investigational Product		
Subcategory: Treatment Assignment/Randomization Error		
Took incorrect study medication	Do not exclude from PPS. Analyze 'As randomized' or 'As assigned'.	Stats and monitor
Subcategory: Compliance		
	Exclude from PPS when occurred during Period 2 prior to use of rescue ixekizumab 80 mg Q2W	Stats

Important Protocol Deviation Category/Subcategory/Study Specific	Action for PPS Analysis	Source to Identify Protocol Deviationa
Subcategory: Patient took medication not fit for use		
	Do not exclude from PPS	Monitor
Subcategory: Unblinding		
	Exclude from PPS	Monitor
Subcategory: Other		
Randomized but did not take any study medication	Exclude from PPS	Stats
Category: Safety		
Subcategory: SAEs		
SAE not reported within designated timeline	Do not Exclude from PPS	Monitor
Category: Informed Consent		
Subcategory: Informed Consent not Obtained/Missing/Lateb		
	Exclude from PPS	Monitor
Subcategory: Improper Consent		
	Do not Exclude from PPS	Monitor
Category: administrative/oversight		
Subcategory: Reg/Ethic Approvals		
	Exclude from PPS	Monitor
Subcategory: Other		
Enrolled in a site with significant GCP non-compliance issue	Exclude from PPS	Monitor

Abbreviations: AE = adverse event; axSpA = axial spondyloarthritis; ASAS = Assessment of Spondyloarthritis International Society; BASDAI = Bath Ankylosing Spondylitis Disease Activity Index; BCG = Bacille de Calmette et Guérin; cDMARD = conventional disease-modifying antirheumatic drug; CRP = C-reactive protein; ECG = electrocardiogram; GCP = good clinical practice; IL = interleukin; ITT = intent-to-treat; IV = intravenous; NSAID = nonsteroidal anti-inflammatory drug; NRS = numerical rating scale; MI = myocardial infarction; mNY = modified New York; MRI = magnetic resonance imaging; PCP = pneumocystis pneumonia; PPS = per protocol set; QIDS = Quick Inventory Depressive Symptomatology; Q2W = every 2 weeks; QIDS-SR16 = Quick Inventory of Depressive Symptomatology–Self-Report 16 items; rad = radiographic; SAE = serious adverse event; TB = tuberculosis; TNF = tumor necrosis factor; V = visit; WBC = white blood cell.

- a The term “Monitor” indicates the protocol deviation will be identified by site monitors and entered into monitor’s list using a spreadsheet. The spreadsheet will be exported as Study Data Tabulation Model (SDTM) DV domain.  
The term “Stats” indicates the protocol deviation will be programmed based on data in clinical database by statistical programmers with the statistical programming guidance provided as the last column. The detailed programming specification will be documented in Analysis Data Model (ADaM) specification.  
The terms “Monitor and Stats” indicates the protocol deviation will be a combination of monitor’s list (SDTM.DV domain) and statistical programming from clinical database, the deviation will show if either source identifies.
- b This deviation will be summarized in CSR table and listing as listed in this document. Issue Management Plan and the monitor’s list is slightly different with subcategory as ‘Informed Consent not Obtained.’ These 2 subcategories will be grouped in the clinical study report table and listing as “Informed Consent not Obtained/Missing/Late.”

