#### **Prior/Concurrent Therapy or Clinical Trial Experience**

- [27] Patients who are taking NSAIDs or cyclooxygenase-2 (COX-2) inhibitors and are not on a stable dose for at least 2 weeks prior to baseline randomization are excluded.
- [28] Have received cDMARDs and/or other therapies such as, but not limited to, gold salts, cyclosporine, azathioprine, dapsone, 6-mercaptopurine, mycophenolate mofetil, or any other immunosuppressive agents within 4 weeks prior to baseline randomization

**Exception:** the following cDMARDs: MTX (oral or parenteral up to 25 mg/week), sulfasalazine (up to 3 g/day), or hydroxychloroquine (up to 400 mg/day) may be allowed IF at stable dose for at least 4 weeks prior to baseline randomization,

AND

if used, are not to be in any combination with other cDMARDs.

**Note:** If MTX is used, local standard of care is to be followed for concomitant administration of folic or folinic acid with MTX.

- [29] Current use of oral corticosteroids greater than 10 mg per day of prednisone or equivalent  
**Note:** If patients are taking prednisone or its equivalent and the dose is less than or equal to 10 mg/day, the dose must be stable for at least 4 weeks prior to baseline randomization.
- [30] Have received any prior, or are currently receiving, treatment with biologic or other immunomodulatory agents, including investigational therapies (such as, but not limited to, Janus kinase inhibitors, TNF inhibitors, IL-1, IL-6, IL-12/23, IL-17 [including ixekizumab], IL-17R, T cell, or B cell targeted therapies)
- [31] Are currently enrolled in, have participated in, or discontinued from a clinical trial involving an investigational product or nonapproved use of a drug or device within the last 30 days prior to screening or a period of at least 5 half-lives of the last administration of the drug (whichever is longer)

- Note:** Investigational products that are biologic or other immunomodulatory agents are not permitted regardless of wash-out period (described in criterion above).
- [32] Are currently enrolled in any other clinical trial involving an investigational product or any other type of medical research judged not to be scientifically or medically compatible with this study
- [33] Are currently receiving or have received treatment with denosumab within 6 months prior to baseline randomization

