### **6.8.2. Concomitant Medications at or after Week 16 for Treatment Modifications (after Completion of Week 16 Assessments)**

*General:*

Changes in therapy are discouraged in the last 8 weeks prior to 52 week assessments.

*NSAIDs and Analgesics:*

Alterations of NSAIDs, including COX-2 inhibitors (dose change, introduction, or withdrawal), are allowed. Doses are recommended to be stable in the 2 weeks prior to an assessment. Any changes in frequency and/or dose must be recorded in the eCRF.

Short-acting analgesics with no anti-inflammatory action (such as paracetamol) are permitted. If administered ad hoc as needed, they are to be withheld within the 24-hour period prior to any assessment. Aspirin (dose not exceeding 350 mg/day) may be taken to manage cardiovascular risk.

Opiate analgesic use: Use of variable doses of opiate analgesics is allowed but is not to exceed an average daily dose of 30 mg morphine or its equivalent.

*Conventional DMARDs:*

Adjustment of allowed cDMARDs (eg, dose change, introduction, withdrawal of cDMARDs, or replacement of a current cDMARD with the introduction of a new cDMARD) is allowed after all assessments at Week 16 are completed. Not more than 1 adjustment of cDMARDs at 1 time within 8 weeks is recommended. cDMARD can only be used as a single agent and not in combination with other cDMARDs. Any changes must be recorded in the eCRF.

For all study periods, the maximum allowed dose is 25 mg/week for MTX, 3 g/day for sulfasalazine, and 400 mg/day for hydroxychloroquine. Local standard of care is to be followed for concomitant administration of folic or folinic acid if MTX is taken and for administration of other cDMARDs.

*Oral corticosteroids:* As of Week 16, adjustments of oral corticosteroids are allowed; however, the maximum dose is not to exceed 10 mg/day of prednisone or its equivalent at any time during these periods.

*Parenteral corticosteroids (intravenous, intramuscular, intra-articular):* As of Week 16, intra-articular injection of corticosteroid may be allowed, as needed. The joint injected must be designated along with the medication in the eCRF and must be recorded as unevaluable on the TJC/SJC assessment.

*Inhaled and topical steroids:* Regular use of inhaled or topical steroids will be permitted during any study period.

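### The per-protocol rule for exclusion [28] has no condition for use of a prohibited agent or for a dose above the protocol cap, so some clear breaches stay in the PPS

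*SAP*

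**What the plan says.** **Protocol 5.2, exclusion [28].** This is a prohibition with a bounded exception. It covers cDMARDs and, among others, "gold salts, cyclosporine, azathioprine, dapsone, 6-mercaptopurine, mycophenolate mofetil, or any other immunosuppressive agents within 4 weeks prior to baseline randomization". The exception reads "MTX (oral or parenteral up to 25 mg/week), sulfasalazine (up to 3 g/day), or hydroxychloroquine (up to 400 mg/day) may be allowed IF" the dose has been stable for at least 4 weeks and no other cDMARD is used with it. Protocol 6.8.2 repeats the same three maxima for all study periods: "the maximum allowed dose is 25 mg/week for MTX, 3 g/day for sulfasalazine, and 400 mg/day for hydroxychloroquine".

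**SAP 6.16, Table RHBX.6.12, row [28].** The row restates the prohibition but carries over neither the exception nor the caps. A patient leaves the PPS in three situations:

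- a stop or dose decrease in the last 3 days ("Exclude from PPS if: 1. Stopped or decreased dose for a current med ≤3 days before randomization");
- a start or dose increase less than 4 weeks before randomisation;
- combination cDMARD use, which has no timing condition.

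**Neighbouring rows.** Row [29] (oral corticosteroids) lists "Dose >10 mg/day any time within 4 weeks" as its first condition. Row [35] (opiates) lists "Doses >30 mg/day any time within 6 weeks before randomization". Rows [30] and [34] exclude outright.

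**Role of the PPS.** SAP 6.1.1 defines the PPS by a subset of important deviations that affect the primary endpoint, so the action column of the table decides who leaves. SAP 6.10.3 uses PPS-16 and PPS-52 to support the primary ASAS40 analysis at Weeks 16 and 52.

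**The concern.** Row [28] is built like row [27], the NSAID row. Protocol [27] only requires a stable dose of a permitted class, so a test for recent change suits it. Protocol [28] is different in kind: for most of the drugs it covers, any use inside the window is the breach, whether or not the dose moved. A recent-change test misses the patient who simply stays on the drug.

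The result is an odd ordering. A patient who lowered a permitted methotrexate dose two days before randomisation is removed. A patient taking azathioprine unchanged through randomisation is kept. A set meant to be free of deviations that bear on ASAS40 would then include patients on background treatment that the protocol rules out, and its value as support for the ITT result would be reduced.

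**Working it through.** The plan gives no figure on this point, so there is none to reproduce. The check applies two rules to the same patient profiles.

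**Rule A, protocol [28] breached:** a non-excepted agent used in the 28 days before randomisation; or an excepted cDMARD above its cap; or an excepted cDMARD not stable for 4 weeks; or cDMARDs in combination.

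**Rule B, removed by SAP row [28]:** a stop or decrease 3 days or less before randomisation; or a start or increase less than 28 days before; or combination cDMARD use.

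| Profile | Breaches protocol [28] | Removed by row [28] |
|---|---|---|
| One prohibited agent, unchanged | yes | **no** |
| One excepted cDMARD above cap, unchanged | yes | **no** |
| Prohibited agent stopped on day -10 | yes | **no** |
| Prohibited agent stopped on day -2 | yes | yes |
| Prohibited agent started on day -14 | yes | yes |
| Two cDMARDs, stable | yes | yes |
| Above cap and in combination | yes | yes |
| Excepted cDMARD within cap, stable | no | no |

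The third line holds for any stop from day -27 to day -4: later than the protocol's 28-day limit, earlier than the row's 3-day limit.

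**Could another row catch these patients?**

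- The Excluded Con-meds row does not reach unchanged use: "Excluded Con-meds refers to clinically meaningful change in con-meds", and that change must occur in Period 2.
- Row [30] excludes prior or current biologic or other immunomodulatory agents, with no time limit. If it covered the drugs in [28], any past use would exclude and the 4-week window in [28] would have no purpose. It would not reach over-cap methotrexate, sulfasalazine or hydroxychloroquine in any case.

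**Possible size.** The documents give no count of such patients. Assume *k* = 1 to 3 per arm, *n* = 100 per arm, and the Week 16 planning rates from SAP 5.2 (46% and 18%). The largest shift arises if every affected patient is a responder:

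shift = (r - k)/(n - k) - r/n

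- 46%: k = 1 gives 45/99 = 45.5%, a fall of 0.5 points; k = 3 gives 43/97 = 44.3%, a fall of 1.7 points.
- 18%: k = 1 gives 17/99 = 17.2%, a fall of 0.8 points; k = 3 gives 15/97 = 15.5%, a fall of 2.5 points.

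If all three were nonresponders, the rates would rise by 1.4 points (46/97 = 47.4%) and 0.6 points (18/97 = 18.6%).

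**The case against.** **The PPS need not remove every eligibility breach.** This is right. SAP 6.1.1 speaks of a subset, many eligibility rows keep the patient, and the SAP revision history shows that the condition for [28] was deliberately updated together with [27], [29] and [35]. A breach of [28] is therefore not, by itself, proof of misclassification. The force of the point comes from comparison within the table: [29] and [35] were revised at the same time and each tests its own limit, while [28] does not.

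**Stable background treatment may matter little.** Protocol 2.1 says that axSpA responds poorly to cDMARDs and systemic corticosteroids, so a dose change near baseline could disturb ASAS40 more than steady use. This has some weight. But the statement does not cover every immunosuppressant, and it names corticosteroids, for which row [29] removes over-limit use anyway.

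**Short stop windows run through the table.** Row [27] uses 3 days, [29] uses 10 and [35] uses 7, each shorter than the protocol window. That makes a tolerance for early stops of *permitted* drugs look deliberate, and it can stand. It does not extend to prohibited use, because [29] and [35] remove over-limit use at any time in the full protocol window.

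**Unseen documents may close the gap.** Programming guidance was moved outside the SAP, and Appendix 13 is redacted. Neither can be checked, so the point is limited to the rule as the SAP states it. Row [28] also lacks the word *only* that opens the action in row [27], but it gives no further condition.

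**Conclusion.** The gap is real on the text and should be closed. Apart from combination cDMARD use, row [28] responds only to recent changes, and the three profiles in the working stay in PPS-16 and PPS-52. The supportive ASAS40 analyses are weakened to that extent. The size rests on an assumed 1 to 3 patients per arm and on the planning rates: at most about 0.5 to 1.7 points at 46% and 0.8 to 2.5 points at 18%.

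The documents do not support several stronger readings that a reader might infer:

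- *That row [28] tests nothing but recent change.* The combination clause has no timing test, so the gap concerns patients on a single agent.
- *That the per-protocol analyses cannot serve as a check.* A few patients would blur them, not void them.
- *That the trial's main result is at risk.* The primary analysis is ITT, and the PPS analyses carry no alpha.
- *That breaches would be hidden.* SAP 6.16 still tabulates and lists them as important deviations.
- *That removing 1 to 3 of 100 patients moves the rate by 1 to 3 points.* Numerator and denominator fall together, so at these rates the movement is smaller.
- *That such patients were enrolled.* Nothing in the documents shows this.

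**What to change.** Reconcile row [28] with protocol exclusion [28]. Add a first condition, parallel to those in rows [29] and [35], that removes a patient with either:

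- any use, within the protocol's 4-week window, of a cDMARD or immunosuppressant outside the protocol exception; or
- use in that window of an excepted cDMARD above the protocol's own maximum.

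Apply the 3-day stop/decrease tolerance only to the three excepted cDMARDs. Keep the start/increase condition and the combination clause. If the sponsor does intend to keep any of the three profiles in the PPS, the row should say so and give the reason.

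The cost is one table cell and its programming, done before unblinding. No new data are needed. The PPS may become slightly smaller; the ITT analysis does not change.
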